## **7. TREATMENT OF TRIAL PARTICIPANTS**

### **7.1 Description of Study Intervention(s)**

The treatment which will be supplied to all participants is a pair of custom, CAD/CAM ethylene vinyl acetate (EVA) foot orthoses (insoles). The insoles are manufactured either from a direct digital scan of the participants feet, or from a foam-box cast of the participants feet which will then be scanned into the CAD/CAM system. This is a standard treatment widely used across Orthotic Services in the UK.

### **7.2 Maintenance and storage of device**

- All Direct Foot scans will be saved by the Co-I in the CAD/CAM insole system at the time of their first appointment, per standard clinical practice.
- All Foam-box casts will be sent by the secure internal NHS mail system to Gartnavel General Hospital to the Orthotic Technician, as per standard clinical practice. The foam-box cast will be scanned and saved by the Orthotic Technician in the CAD/CAM insole system, per standard clinical practice.
- All digital models will also be available for repeat prescriptions for participants attending the NHS GGC Orthotic department again in future once they return to standard care.
- Following manufacture, all physical insoles will be delivered to GGH Orthotic Administrators, as per standard NHS GGC Orthotic Department process.
- All insoles will be placed into clear plastic bags with the participant name and date of appointment attached. No other paperwork will be send to GRI with the insoles.
- Insoles will be sent to the GRI Orthotic Department using a secure internal courier, as per standard clinical practice.
- The Co-I will double check the insoles on arrival at GRI to ensure that only the participant name and date of appointment is contained in the bag with the insoles. It is standard practice for the Orthotist on site at GRI to double check the incoming goods for appointments.
- As per standard practice in the NHS GGC Orthotic Service, the insoles will be stored in the locked in an Orthotic Appointments Cupboard in Glasgow Royal Infirmary until the time of the participant fitting appointment.

### **7.3 Compliance with Trial treatment**

Participant compliance with the trial treatment will be assessed at the Third Appointment, Fourth Appointment and Fifth Appointment by means of discussion with the participant regarding their use of the insoles over the preceding 4-weeks, and by collection of their diary of daily wear time.

### **7.4 Concomitant Medication**

There are no contraindicated medications within the trial design. No medication changes are anticipated as a result of participating in this trial.

#### 7.5 Post-trial treatment

All participants will be offered the opportunity to retain and continue use of the medical device (CAD/CAM insoles) after their participation in the trial has concluded.

## 8. SAFETY REPORTING

### 8.1 Definitions

|  |   |
|--|---|
| Adverse events (AE)                 | 
An adverse event is any untoward medical occurrence, unintended disease or injury, or untoward clinical signs (including abnormal laboratory findings) in subjects, users or other persons, whether or not related to the investigational medical device.
 
Note 1 to entry: This definition includes events related to the investigational medical device or the comparator.
 
Note 2 to entry: This definition includes events related to the procedures involved.
 
Note 3 to entry: For users or other persons, this definition is restricted to events related to the use of investigational medical devices.
  |
| Serious Adverse Event               | 
An adverse event that led to any of the following:
 

a. death,

b. serious deterioration in the health of the subject, users or other persons as defined by one or more of the following:

1. a life-threatening illness or injury, or

2. a permanent impairment of a body structure or a body function including chronic diseases, or

3. in-patient or prolonged hospitalisation, or

4. medical or surgical intervention to prevent life-threatening illness or injury or permanent impairment to a body structure or a body function,

c. foetal distress, foetal death or a congenital abnormality or birth defect including physical or mental impairment

 
Note 1 to entry: Planned hospitalisation for a pre-existing condition, or a procedure required by the protocol, without serious deterioration in health, is not considered a serious adverse event.
 |
| Serious adverse device event (SADE) | A serious adverse device effect (SADE) is any adverse device effect that has resulted in any of the consequences characteristic of a serious adverse event. A SADE may be anticipated or  |

|  |  |
|--|--|
|  | unanticipated.   |
| Unanticipated Serious Adverse Device Effect (USADE) | Unanticipated serious adverse device effect (USADE) is a serious adverse device effect which by its nature, incidence, severity or outcome has not been identified in the current version of the risk analysis report. |

## **8.2 Recording and Reporting of Adverse Events**

AEs must be recorded, assessed, reported, analysed and managed in accordance with the Research Governance Framework for Health and Community Care and the study protocol. All AEs must be assessed for seriousness. AEs for this study will be recorded within the participant's notes but are not considered reportable.

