| Secondary Objectives | 

1. To compare the changes in foot function in two groups of participants fitted with custom CAD/CAM insoles manufactured using different foot shape capture methods

2. To compare the changes in foot health in two groups of participants fitted with custom CAD/CAM insoles manufactured using different foot shape capture methods

3. To compare the participant satisfaction in two groups of participants fitted with custom CAD/CAM insoles manufactured using different foot shape capture methods

4. To compare the time-in-transit and cost-time analysis of the custom CAD/CAM insoles manufactured using different foot shape capture methods

5. To compare the environmental impact of custom CAD/CAM insoles manufactured using different foot shape capture methods

 |
| Tertiary Objectives  | 

1. Recruitment rate

2. Participant compliance with the study protocol / Adherence

3. Adverse events

4. Drop-out rate

  |

|  |  |
|--|--|
| Device Type                                | Custom, Computer aided design (CAD) Computer aided manufacture (CAM), Ethylene-vinyl acetate (EVA) Foot Orthoses (insoles)   |
| Manufacturer Name                          | Manufactured in the NHS Greater Glasgow and Clyde Orthotic Department, at Gartnavel General Hospital. Manufactured using the Paromed Paromanager CAD/CAM system  |
| Principle intended use                     | For the use of any persons with a medical condition or lower limb biomechanical deficit which would commonly be treated with the use of insoles, as per the NHS GGC MSK Foot and Ankle Pathway:
http://www.clinicalknowledgepublisher.scot.nhs.uk/Published/PathwayViewer.aspx?fileId=119 |
| Length of time the device has been in use. | These devices are currently used as a standard care across NHS services in the UK, and have been for many years. Both methods of shape-capture are standard clinical practice across the UK. No novel techniques or devices are under investigation within this trial.   |

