| of the custom CAD/CAM insoles manufactured using different foot shape capture methods   | transit and delivery times associated with each arm of the trial will be compared.
Cost analysis – Costs relating to time-in-transit for each arm of the trial will be compared   |  |
| 5. To compare the environmental impact of custom CAD/CAM insoles manufactured using different foot shape capture methods                | 5. Analysis of annual custom insole production in NHSGGC in relation to the environmental impact of the required phenolic foam production  and carbon footprint of transportation from manufacturer to digital upload of foam-box cast using carbon foot print calculations  . | 5. Calculated retrospectively from April 2021 – April 2022   |
| Tertiary Objectives

Assessment of factors over a defined 9-month recruitment period including:

1. Recruitment rate | 1. Recruitment rate = $n/\text{recruitment period}$  | 1. Throughout recruitment period and calculated at the trial conclusion                                |
| 2. Participant compliance with the study protocol / Adherence   | 2. Participants will keep a diary of daily wear time, in accordance with prior publications on measuring Orthotic Adherence  . The minimum threshold for adherence is >21 hours per week   | 2. Data collected from participants at the third appointment, fourth appointment and fifth appointment |
| 3. Adverse events   | 3. Adverse events  | 3. Self-reported by participants at any time throughout the trial period                               |
| 4. Drop-out rate  | 4. Dropout rate = $n \text{ dropout}/\text{duration of trial}$   | 4. Collected throughout trial and calculated at trial conclusion                                       |

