#### Adverse events:-

Adverse events reported by participants at any time during the trial will be addressed as outlined in section 8 of this protocol.

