## **6.7     Source Data**

Source documents are original documents, data, and records from which participants' Case Report Form (CRF) data are obtained. These include, but are not limited to, hospital records (from which medical history and previous and concurrent medication as specified at each of the participant appointments in section 6 of this protocol, may be summarised into the CRF), diaries, medical imaging reports for relevant radiographs of the foot, MRI of the foot and CT of the foot, and correspondence from the participant. CRF entries will be considered source data if the CRF is the site of the original recording (e.g., there is no other written or electronic record of data). In this study the CRF will be used as the source document for FSHQ data, OPUS data, physical assessment data, and diary of insole wear time data. All other participant information will be sourced from verifiable from source documents (e.g. hospital records, diaries, medical imaging reports for relevant radiographs of the foot, MRI of the foot and CT of the foot, and correspondence from the participant).

All CRF documents will be stored safely in a locked filing cabinet in the Glasgow Royal Infirmary. On all study-specific documents, other than the signed consent form, the participant will be referred to by the unique participant number, not by name.

Source data verification ensures accuracy and credibility of the data obtained. The PI will review the reported data to ensure they are accurate, complete, and verifiable from source documents. All data reported on the CRF will be supported by source documents. Data Verification will be carried out by the PI who will check the CRF for completeness and clarity, and crosscheck them with source documents

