## **8.3 Recording and Reporting of Serious Adverse Events**

Where an SAE requires recording; full details including the nature of the event, start and stop dates, severity, causal relationship to the device and/or trial procedures, and the outcome of the event will be recorded in the participant's medical notes. These events will be monitored and followed up until satisfactory resolution and stabilisation.

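### Adverse events are a named outcome, but no scheduled contact asks about them in a standard way, so new problems in participants who keep wearing the insoles are likely to be under-counted

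*Combined protocol and SAP*

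**What the plan says.** The synopsis lists "3. Adverse events" among the tertiary objectives, and the table in section 5 repeats it as an outcome measure. The timing column of that table gives the only method of finding events: "Self-reported by participants at any time throughout the trial period". The data collection summary in section 6.1 is similar: "Adverse events reported by participants at any time during the trial will be addressed as outlined in section 8".

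Section 8.2 first sets a general duty, "AEs must be recorded, assessed, reported, analysed and managed", and then states the arrangement for this trial: events go in the participant's "notes but are not considered reportable". For serious events, section 8.3 says that full details "will be recorded in the participant's medical notes".

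Section 6.4.5 scripts each contact in numbered steps, and Appendix 4 tabulates them. Neither contains an adverse event item. Section 9.1 covers the FHSQ and OPUS scores only.

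**The concern.** A named outcome needs a way of being found, a place to be recorded and a planned summary. Here the first is passive, the second is the clinical notes with no stated onward step for non-serious events, and the third is absent, although section 8.2 itself calls for analysis.

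Passive report tends to miss problems that a participant regards as minor or does not link to the insoles. Events nobody asked about cannot be reliably recovered once follow-up is over. The trial is described as an equivalence trial of two ways of capturing foot shape. If the same share of events is missed in each arm, the absolute difference between arms shrinks, and the two methods look more alike in tolerability than they are.

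**Working it through.** **1. What is asked at each contact (section 6.4.5, compared with Appendix 4).**

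| Contact | Scripted questions and checks | Adverse event question | Adverse event row in Appendix 4 |
|---|---|---|---|
| Second (fitting) | 10-minute wear check, FHSQ, medication changes | none | none |
| Third (4 weeks) | ability to wear, FHSQ, wear time, medication changes | none | none |
| Fourth (8 weeks) | ability to wear, FHSQ, wear time, medication changes | none | none |
| Fifth (12 weeks) | ability to wear, FHSQ, OPUS, wear time, medication changes | none | none |

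The scripts are detailed enough to include reminder calls, so the lack of an adverse event step is not just a matter of brevity.

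**2. Where an event goes once it is known.**

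- It leads to withdrawal: the reason is entered in the CRF (section 6.6).
- It is a fitting problem: the adjustment is entered on the Excel sheet (section 6.4.5), as an adjustment and not as an adverse event.
- It is a serious device-related event meeting the criteria of section 8.4: it is reported to the sponsor's pharmacovigilance office within 24 hours, with a copy in the Study Site File.
- It is a non-serious event in someone who carries on: it goes in the participant's notes (section 8.2). The steps that name Excel entries cover insole elements, assessment findings, adjustments, FHSQ, OPUS and wear time (sections 6.4.3 and 6.4.5). None names adverse events.

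The last group is the one at risk, first of not being mentioned and then of not being carried over.

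**3. Illustration of scale.** The plan has no adverse event figure to reproduce. The arm size comes from section 9.2: 54/0.95 = 56.8, rounded up to 57, and 2 × 57 = 114. The risk p, the capture fraction c (the share of affected participants whose event becomes known) and the two-sided 5% level used below are all assumptions.

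Participants with an event seen = 114 × p × c.

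- p = 0.10: 114 × 0.10 = 11.4 affected. With c = 0.75, 8.55 are seen and 2.85 missed. With c = 0.50, 5.7 are seen and 5.7 missed.
- p = 0.20: 114 × 0.20 = 22.8 affected. With c = 0.75, 17.1 are seen and 5.7 missed. With c = 0.50, 11.4 are seen and 11.4 missed.

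With equal capture in both arms, the observed difference is c × (p2 − p1). Take true risks of 10% and 30%. The power with 57 per arm, by the normal approximation with pooled variance under the null, is Φ[(d − 1.96 × SE0)/SE1]. Here d = 0.20c, SE0 = √(2p̄(1 − p̄)/57), p̄ is the mean of the two observed risks, and SE1 is the unpooled standard error.

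- c = 1: (0.20 − 1.96 × 0.0749)/0.0725 = 0.73, power 77%.
- c = 0.75: power 61%.
- c = 0.50: (0.10 − 1.96 × 0.0562)/0.0554 = −0.18, power 43%.
- c = 0.25: power 23%.

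For an event with a true risk of 5%, the chance of seeing none in an arm of 57 is (1 − 0.05c)^57. This is 5% at c = 1, 11% at c = 0.75, 24% at c = 0.50 and 49% at c = 0.25.

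These figures show the direction and how sensitive the result is to c. They do not estimate what will happen in this trial.

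**The case against.** The strongest reply is that this is a low-risk trial of standard-care insoles in both arms, that adverse events rank as a tertiary item beside recruitment and drop-out, and that no between-arm comparison of them is planned. The contacts also prompt to some extent. Problems during the trial wear at fitting are dealt with, inability to wear the insoles is established at each call, and section 7.3 has the investigator discuss insole use over the preceding four weeks. Self-report at any time does not forbid prompting. All of this stands and limits the consequence, but it does not supply a standard question, so a participant with a new problem who still wears the insoles need never be asked.

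Several stronger readings are tempting, and the documents do not support them.

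- *Nobody asks about problems.* The fitting check and the inability-to-wear step are partial prompts, though neither is recorded as an adverse event.
- *Adverse events bypass the trial dataset.* Section 13 says in general terms that study data go to the Excel sheet, the routes in step 2 of the working exist, and the CRF template (Appendix 3) is listed but not available here, so a field for events cannot be ruled out.
- *Section 6.7 shows that the CRF omits them.* The sentence "the CRF will be used as the source document for FSHQ data, OPUS data, physical assessment data, and diary of insole wear time data" names the items for which the CRF is the original record. It is not a list of CRF contents, and the same section lets other CRF data come from hospital records.
- *Ordinary adverse events drive the stopping criterion in section 9.4.* That criterion concerns serious events caused by the insoles, which have their own recording, causality and reporting rules in sections 8.3 and 8.4.
- *Calling events non-reportable is itself the error.* Read with section 8.4, it most naturally means not reportable to the sponsor, which is not a fault in itself.

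**Conclusion.** The point holds in a limited form. A named outcome rests on spontaneous report, with no standard question at four contacts where other questions are already scripted, no explicit step from the notes to the data sheet for non-serious events, and no planned summary. The likely result is a low count, concentrated among participants who have a new problem and continue. The intended blinding of participants and PI should keep under-capture similar between arms, so the harm is lost events and a weaker view of any difference in tolerability, rather than bias towards one method.

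The size cannot be derived, because the documents give neither an event rate nor a capture fraction. The primary pain comparison is not affected. That passive report loses events is a well-founded inference, not something the documents measure. The change is a cheap improvement that should be made, and it works only for contacts that have not yet taken place.

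**What to change.** Add one identically worded question on new problems since the last contact to the second, third, fourth and fifth appointments in section 6.4.5, asked by the blinded PI in both arms. Placing it before the step that establishes whether the insoles can be worn would also capture those who leave at that point. Record date, nature, seriousness and relatedness on the CRF and the data sheet against the participant number, add an adverse event row to Appendix 4, and state in section 9.1 that the number of participants with at least one event will be reported by arm. The wording on non-reportability to the sponsor need not change.

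The cost is about a minute (assumed) at each existing contact: 114 × 4 = 456 contacts, or 456/60 = 7.6 hours over the whole trial, plus one CRF record. No visit or staff member is added, and the blind is unaffected. The downside is that more minor events will be recorded.

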## **8.3 Recording and Reporting of Serious Adverse Events**

Where an SAE requires recording; full details including the nature of the event, start and stop dates, severity, causal relationship to the device and/or trial procedures, and the outcome of the event will be recorded in the participant's medical notes. These events will be monitored and followed up until satisfactory resolution and stabilisation.

### **Assessment of causality**

I.e., does the event have a "reasonable causal relationship" with any trial specific procedures or the investigational device?

The assessment of causality must be carried out by the PI or other medically qualified local investigator.

### **Assessment of expectedness**

If the SAE is considered related to any trial specific procedures or the investigational medical device an assessment should be made of the expectedness i.e., is the SAE a recognised adverse effect of the investigational medical device or a trial procedure.

## **8.4 Reporting to Sponsor**

The following events defined are considered reportable to the sponsor.

- Any Serious Adverse Event that is considered related to the trial specific procedures, or the medical device(s) that is considered unexpected by the Chief Investigator or their delegate. (USADE)
- Any device related serious adverse event that led or may have led to one of the following outcomes: (SADES)
  - The death of a participant
  - A serious deterioration in the health of a participant.
  - A serious deterioration in health may include (non-exhaustive):
    - Life threatening illness
    - Permanent impairment of a body function or permanent damage to a body structure
    - A condition necessitating medical/surgical intervention to prevent a) or b)
    - Foetal distress or death, or any congenital anomalies or birth defects.

SAEs meeting the above criteria must be reported to the Pharmacovigilance Office immediately (within 24 hours) using the SAE form for a non CTIMP found here: <https://glasgowctu.org/Home/00-safety-reporting/>. The SAE form should be completed and signed by appropriately delegated staff. The form should be e-mailed to the PV Office ([contact]) and a copy placed in the Study Site File.

If all the required information is not available at the time of initial reporting, the CI (or designee) must ensure that any missing information is forwarded to the PV Office as soon as this becomes available. The report should indicate that this information is follow-up information for a previously reported event.

### **8.5 Reporting of USADEs to the REC**

The Sponsor will report all USADEs to the ethics committee within 15 days of the PV office becoming aware of the event, via the 'report of serious adverse event form' for non-CTIMPs published on the Health Research Authority web site.

[https://www.hra.nhs.uk/documents/2466/Non\\_CTIMP\\_Safety\\_Report\\_Form\\_Accessible\\_September\\_2020\\_AA.odt](https://www.hra.nhs.uk/documents/2466/Non_CTIMP_Safety_Report_Form_Accessible_September_2020_AA.odt)

The form should be completed in typescript and signed by the Chief Investigator.

### **8.6 Reporting of SADEs and USADES to IRIC**

The CI or delegate must submit reports relating to the medical device that meet the above criteria to the Incident Reporting and Investigation Centre (IRIC – part of NHS National Services Scotland). Information about how to report an adverse incident can be found here: <http://www.hfs.scot.nhs.uk/online-services/incident-reporting-and-investigation-centre-iric/how-to-report-an-adverse-incident/>

